5.2.2 Dose Delay

Retreatment following treatment interruption for treatment-related toxicity or at the start of a new cycle may not occur until all of the following parameters have been met:

- Platelet count $\geq 50,000/\text{mm}^3$
- ANC $\geq 1000/\text{mm}^3$ and no fever
- Grade 3 or higher treatment-related non-hematologic AEs (including nausea, vomiting, diarrhea, and hypertension only if persisting despite optimal medical treatment), with the exception of alopecia, have recovered to Grade ≤ 1 or baseline (or, at the investigator's discretion, Grade ≤ 2 if not considered a safety risk for the patient)

If a treatment delay results from decline in hematologic parameters, the frequency of blood count assessments should be increased as clinically indicated. G-CSF (Filgrastim or Peg-filgrastim) may be given for neutropenia at the investigator's discretion.

If these parameters are met within 2 weeks of treatment interruption or cycle delay, treatment may be resumed. Please see Section 5.2.3 for dose reductions at the time of treatment resumption.

If these parameters have not been met after 2 weeks of dosing interruption (including the scheduled 1 week off Palbociclib treatment) or 2 weeks of cycle delay, permanent treatment discontinuation should be considered. Treatment resumption for patients recovering from toxicity after > 2 weeks of treatment interruption or cycle delay but deemed to be deriving obvious clinical benefit per the investigator's best medical judgement is left at the investigator's discretion.

A new cycle only starts when the criteria listed above are met and treatment with palbociclib \pm carboplatin may be administered. Otherwise, initiation of the new cycle must be delayed until such criteria are met. In the event that the start of a new cycle is delayed due to treatment related toxicity, procedures required on Day 1 of the given cycle will be performed when palbociclib \pm carboplatin is resumed. New Day 1 procedures that were performed prior to knowing the need to delay the start of the cycle do not need to be repeated 1) if not required to

determine whether study drugs may be resumed and 2) if performed within 7 days prior to study drug resumption.

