5.2.3 Dose Reductions

Following dosing interruption or cycle delay, the dose of the study drugs may need to be reduced when treatment is resumed.

No specific dose adjustments are recommended for Grade 1/2 treatment-related toxicity.

Dose reduction of palbociclib and carboplatin by 2 dose levels will be allowed depending on the type and severity of toxicity encountered (Table 3 and 4). Patients requiring more than 2 dose reductions will be discontinued from the study and entered into the follow-up phase.

Once a dose has been reduced for a given patient, all subsequent cycles should be administered at that dose level, unless further dose reduction is required. Dose re-escalation is not allowed.

Table 3: Study Drug Dose Levels

Palbociclib Dose Levels

Dose Level	Dose	Dispensed as
0 (starting dose)	125 mg daily, days 1-14	125 mg capsules OR 5 mL solution
-1	100 mg daily, days 1-14	100 mg capsules OR 4 mL solution
-2	75 mg daily, days 1-14	75 mg capsules OR 3 mL solution

Carboplatin Dose Levels

Dose Level	Dose
0 (starting dose)	AUC= 5, day 1
-1	AUC= 4, day 1
-2	AUC= 3, day 1

Table 4: Dose Modifications for Treatment Related Toxicities Requiring Treatment Interruption/Delay or Persisting Despite Optimal Medical Treatment

Toxicity	Restart Palbociclib Treatment at:	Restart Carboplatin Treatment at:
Uncomplicated Grade 3 neutropenia (ANC <1000/mm ³)	Same dose level	Same dose level
Grade 3 neutropenia (ANC <1000/mm ³) associated with a documented infection or fever ≥ 38.5° C	↓ 1 dose level	↓ 1 dose level

Grade 4 neutropenia ($ANC < 500/mm^3$)	↓ 1 dose level	↓ 1 dose level
Grade 4 thrombocytopenia (platelet count $< 25,000/mm^3$)	↓ 1 dose level	↓ 1 dose level
Grade ≥ 3 non-hematologic toxicity (including nausea, vomiting, diarrhea, and hypertension only if persisting despite optimal medical treatment)	↓ 1 dose level	↓ 1 dose level
Note: G-CSF (Filgrastim or Peg-filgrastim) may be added for low ANC at treating physician's discretion.		

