6.0 STUDY PROCEDURES

6.1 Time and Events Table

6.1.1 Calendar

	Screening ¹	Treatment										Maintenance	Every 8 weeks from Cycle 7, Day 1	End of Treatment	Survival
		Cycle 1			Cycle 2		Cycle 3	Cycle 4	Cycle 5	Cycle 6	Cycle 7				
Day of Cycle		1	8	14	1	14	1	1	1	1	1	1	EOT ⁹	Survival ¹⁰	
Informed Consent	X														
Demographics	X														
Inclusion/Exclusion Criteria	X														
Tumor Biopsy for Correlative Analysis ¹⁴	X														
Interim Biopsy for Correlative Analysis ^{12,16}						X ³									
Tumor Biopsy to confirm progression ^{15,16}													X		
H&P, Relevant Medical History	X														
Pregnancy Test	X	X													
Clinic Visit ⁴	X	X		X ^{2,13}		X ^{2,13}	X								
Performance Status	X	X		X ^{2,13}		X ^{2,13}									
Physical Exam ⁴	X	X		X ^{2,13}		X ^{2,13}									
QOL Survey ⁴		X		X ^{2,13}		X ^{2,13}									
Adverse Effects Assessment ⁵		X		X ^{2,13}		X ^{2,13}	X								

	Screening ¹	Treatment										Maintenance		Every 8 weeks from Cycle 7, Day 1	End of Treatment	Survival
		Cycle 1			Cycle 2		Cycle 3	Cycle 4	Cycle 5	Cycle 6	Cycle 7	Cycle 8+				
Day of Cycle		1	8	14	1	14	1	1	1	1	1	1	EOT ⁹	Survival		
CBC ⁶	X	X		X ²	X ^{2,13}	X ²	X ^{2,13}		X							
CMP ⁶	X	X			X ^{2,13}		X ^{2,13}		X							
Correlative: Salivary Rinse ⁷		X	X ²		X ^{2,13}		X ^{2,13}									
Correlative: 2 Serum Tubes ⁷		X	X ²		X ^{2,13}		X ^{2,13}									
Correlative: 1 Serum Tube ⁷		x														
CT Imaging ⁸	X						X ³		X ³		X ³		X ³			
Palbociclib Dosing ¹¹		125 mg daily, days 1-14. Cycle Length: 21 Days										125 mg daily, days 1-21. Cycle Length: 28 Days				
Carboplatin Infusion		X			X		X	X	X	X						
Survival Assessment														X ¹⁰		

1= May be performed within 28 days of Cycle 1, Day 1 unless otherwise specified

2= May be performed +/- 4 days

3= May be performed +/- 7 days

4= Vital signs, physical exam, ECOG performance status will be checked at each visit as well administration of FACT H&N questionnaire (see Appendices B and C)

5= Toxicities will be evaluated using CTCAE version 4.03

6= Labs will be obtained pre-dose. CMP includes Basic Metabolic Profile (Na, K, Cl, CO2, BUN, Cr, Glu), AST/SGOT, ALT/SGPT, Alk Phos, T Bili, Albumin, Ca, and Total Protein

7= Collection tubes (see lab manual) will be drawn and sent to the [name] lab for DNA isolation and long term storage. May be performed +/- 4 days

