9.0 DRUG INFORMATION

9.1 Carboplatin

- Other names for the drug: Carboplatin (Paraplatin ®)
- Description: IV Medication. Vial sizes of 50 mg/5 mL, 150 mg/15 mL, 450 mg/45 mL, 600 mg/60 mL all in individually packaged multi-dose vials.
- Classification - type of agent: Cytotoxic/Alkylating-Like Compound
- Mode of action: Carboplatin produces interstrand DNA cross-links which in turn interfere with mitosis. DNA damage leads to attempts at DNA repair however, when repair is not possible apoptosis is activated, especially in the case of double strand DNA breaks.
- Pharmacokinetics: Carboplatin exhibits linear pharmacokinetics with Cmax and AUC increasing linearly with dose.
 - Half-life- Plasma levels of intact carboplatin decay in a biphasic manner with a half-life of 2.6-5.9 hours.
 - Elimination- The major route of elimination is renal excretion. The primary determinant of carboplatin clearance is glomerular filtration rate
 - Metabolism- Minimally hepatic to aquated and hydroxylated compounds
- Side effects:
 - The most common adverse reactions (incidence \geq 10%) are bone marrow suppression (anemia, thrombocytopenia, and/or neutropenia), nausea, vomiting, mild elevations in alkaline phosphatase, and mild decreases in serum electrolyte values
 - Hypersensitivity to carboplatin has been reported in 2% of patients. These allergic reactions have been similar in nature and severity to those reported with other platinum containing compounds and have been successfully managed with standard epinephrine, corticosteroid, and antihistamine therapy
 - Please refer to the package insert for a comprehensive list of adverse events.
- Drug Interactions:
 - Fosphenytoin/Phenytoin- Carboplatin may decrease serum concentrations of these drugs hence monitor therapy
- Storage and stability:
 - Unopened vials of carboplatin are stable to the expiration date indicated on the

package when stored at 25°C (77°F); excursions permitted from 15°C-30°C (59°-86°F). Protect from light

- Multidose vials maintain microbial, chemical, and physical stability for up to 14 days at 25°C following multiple needle entries
- Parenteral drug products should be visually inspected for particulate matter and discoloration prior to administration. Solutions for infusion should be discarded 8 hours after preparation
- Administration:

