9.2 Palbociclib

- Other names for the drug: Palbociclib (Ibrance ®)
- Description: Oral Medication. Supplied as capsules which must be swallowed or solution which may be swallowed or administered via feeding tube (ie nasogastric tube or PEG). Capsules are supplied in 125 mg, 100 mg, 75 mg doses. Bottles consist of 21 tablets. Solution is supplied at a concentration of 25 mg/mL and 112 mL are in each bottle
- Classification - type of agent: Cyclin-dependent kinase (CDK) 4 and 6 inhibitor
- Mode of action: Palbociclib is an inhibitor of CDK 4/6. Cyclin D1, CDK 4, and CKD 6 are downstream signaling pathways which lead to cellular proliferation. In vitro, palbociclib reduced cellular proliferation of estrogen receptor-positive breast cancer cell lines by blocking the progression of the cell from G1 into S phase of the cell cycle.
- Pharmacokinetics:
 - Absorption- The mean time to reach maximum concentration (Tmax) is between 6-12 hours following oral administration. The mean bioavailability of palbociclib after an oral 125 mg dose is 46% and in the dosing range of 25-225 mg the AUC and Cmax increased proportionally with dose in general. Steady state was achieved within 8 days following repeated once daily dosing. In studies utilizing capsules, food intake reduced the intersubject variability of palbociclib exposure therefore the palbociclib capsules should be taken with food. Pharmacokinetic studies of the solution demonstrate no change in the variability of palbociclib exposure with food administration. Therefore, palbociclib solution may be taken with or without food.
 - Half-life- The plasma elimination half-life is 29 (+/- 5) hours in patients with advanced breast cancer
 - Metabolism- Palbociclib undergoes hepatic metabolism in humans. The primary metabolic pathways for palbociclib involve oxidation and sulfonation. CYP3A and

SULT2A1 are mainly involved in the metabolism of palbociclib. Palbociclib is a weak time-dependent inhibitor of CYP3A following daily dosing to steady state.

- Elimination- Fecal elimination is the major route of excretion (74.1%) with an additional 17.5% recovered in urine. The majority of excreted materials were metabolites
- Side effects:
 - The most common adverse reactions (incidence \geq 10%) are neutropenia, leukopenia, infections, fatigue, nausea, anemia, stomatitis, headache, diarrhea, thrombocytopenia, constipation, alopecia, vomiting, rash, and decreased appetite
- Drug Interactions:
 - None applicable

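### Section 9.2 says palbociclib has no relevant drug interactions, yet its own pharmacokinetic text describes two CYP3A routes for one

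*Combined protocol and SAP*

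**What the plan says.** Section 9.2 covers palbociclib pharmacokinetics and interactions within one list. Its metabolism item names CYP3A first and continues: "SULT2A1 are mainly involved in the metabolism of palbociclib. Palbociclib is a weak time-dependent inhibitor of CYP3A following daily dosing to steady state". Its absorption item states that "in the dosing range of 25-225 mg the AUC and Cmax increased proportionally with dose in general". Under Drug Interactions, the whole entry is "None applicable".

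Section 9.1 has the same heading for carboplatin. There it names fosphenytoin and phenytoin, with the advice "Carboplatin may decrease serum concentrations of these drugs hence monitor therapy".

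Three other parts of the protocol bear on the point:

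- **Co-medication.** Section 5.3.5 leaves other supportive drugs to the treating physician's discretion.
- **Pointers to other documents.** Sections 1.2 and 8.2 send the reader to the Investigator's Brochure or prescribing information for safety information in general.
- **Dose rules.** Section 5.2.3 sets palbociclib levels of 125, 100 and 75 mg and carboplatin levels of AUC 5, 4 and 3. For grade 4 neutropenia, Table 4 lowers both drugs by one level. The section adds "Dose re-escalation is not allowed".

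**The concern.** The metabolism text and the interaction entry cannot both stand. If CYP3A is a main clearing enzyme, a drug that inhibits or induces it could raise or lower palbociclib exposure. If palbociclib itself inhibits CYP3A, it could raise exposure to a CYP3A substrate. The entry denies both.

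The physician who decides on co-medication under Section 5.3.5 would naturally look at the interaction entry, and it gives no reason to look further. Bone marrow suppression is a common reaction to both study drugs (Sections 8.1.4 and 8.2.3). An unrecognised rise in palbociclib exposure could therefore look like ordinary treatment toxicity. If it contributed to grade 4 neutropenia, both drugs would go down a level and stay there, even after the interacting drug was stopped. More than two reductions ends study treatment. Palbociclib also continues as maintenance after six cycles, which lengthens the period in which a relevant co-medication could be started.

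**Working it through.** The plan states no figure on this point, so there is none to reproduce. The check is a comparison of texts, followed by a yardstick from the protocol's own dose levels.

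**1. Texts side by side**

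| Place | Content | Implication |
|---|---|---|
| 9.2, metabolism | CYP3A is one of two main enzymes | A CYP3A inhibitor or inducer may change palbociclib exposure |
| 9.2, metabolism | Palbociclib is a weak time-dependent CYP3A inhibitor at steady state | Palbociclib may change exposure to a CYP3A substrate |
| 9.2, interactions | "None applicable" | Neither direction is acknowledged |
| 9.1, interactions | Fosphenytoin and phenytoin are named | The heading covers drugs from outside the trial |

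The carboplatin row rules out the charitable reading that the entry means only that the two study drugs do not interact with each other.

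**2. Is the entry corrected elsewhere?** The exclusion criteria in Section 3.2 name no CYP3A drugs. The visible items of Section 5.3 cover supportive drugs, anti-emetics, G-CSF and physician discretion. The pointers in Sections 1.2 and 8.2 do not mention interactions. No visible text corrects the entry.

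This search has a limit. Numbering in Section 5.3 jumps from 5.3.1 to 5.3.4, and an item numbered 8.2.4.1 sits under 8.2.3. A similar jump in Section 10.1.1, from 10.1.1.1 to 10.1.1.4, shows that items may be missing from the available text. Silence in 5.3 and 8.2 is therefore a low-confidence observation. The entry in 9.2 is present and can be read directly.

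**3. Yardstick for a relevant exposure change.** The inputs are the starting dose of 125 mg, level -1 ("100 mg daily, days 1-14") and level -2 at 75 mg, all from Table 3. Exposure is taken as proportional to dose over 25–225 mg, as Section 9.2 says is generally so.

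- Fall equal to one level: 100/125 = 0.80, or 20% lower.
- Fall equal to two levels: 75/125 = 0.60, or 40% lower.
- Rise that cancels level -1: 125/100 = 1.25, or 25% higher.
- Rise that cancels level -2: 125/75 = 1.67, or 67% higher.

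The carboplatin step that Table 4 couples to the palbociclib step is 4/5 = 0.80, also 20% lower. These ratios show how large an interaction would have to be to match the protocol's own dose steps. They do not estimate any interaction.

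**The case against.** The strongest reply accepts the drafting inconsistency and disputes its importance.

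- **Clinical relevance is inferred.** Section 9.2 names a second main enzyme and calls the inhibition weak. A metabolic route shows that an interaction is possible, not that it matters clinically. This is correct, and it is why no effect size is claimed. But the word weak qualifies only the effect of palbociclib on other drugs, not the role of CYP3A in clearing palbociclib. If the sponsor judged the interactions unimportant, the entry should say so.
- **The dose ratios would be the same with no interaction at all.** Also correct. They carry no weight in judging how serious the point is.
- **The path to harm is conditional.** It needs a relevant co-medication, a material exposure change, failure to recognise it, and severe toxicity. Safeguards exist: for blood tests, "Labs will be obtained pre-dose" (Section 6.1.1, note 6), and Section 5.2.2 says "Retreatment following treatment interruption for treatment-related toxicity or at the start of a new cycle may not occur until" ANC and platelet thresholds, among other conditions, are met. G-CSF is allowed, and uncomplicated grade 3 neutropenia restarts at the same dose. These measures limit harm, but none looks for a co-medication as the cause.
- **Sites have the Brochure and the label.** This softens the effect without correcting the entry. Section 9.2 itself confines palbociclib to use as the protocol directs, so the protocol's own statement should be right.
- **Interaction text may exist in parts of 5.3 or 8.2 that are not visible.** Possible, but Section 9.2 would then contradict that text as well.

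**Conclusion.** The concern holds. The interaction entry is an affirmative statement that its own section contradicts, and this can be seen from Section 9.2 alone. Confidence is high for that entry and low for any claim that Sections 5.3 and 8.2 are silent.

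The size of the consequence cannot be given, because the documents state neither the exposure change nor how often patients take a relevant drug. The yardstick of a 20% fall or a 25% rise for one dose level rests on dose proportionality holding as Section 9.2 states.

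This is a patient-safety and consistency point that should be corrected. It does not touch the endpoint, the sample size, the two-stage decision rule or the analysis.

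**What to change.** Replace the entry in Section 9.2 with a statement that CYP3A inhibitors, inducers and substrates may interact with palbociclib, with the content taken from the current Investigator's Brochure or prescribing information. Unless Section 5.3 already contains one, add a line there requiring co-medication to be reviewed for CYP3A interactions before and during palbociclib, including maintenance. Which drugs to avoid or adjust is a clinical decision for the sponsor.

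The cost is a text amendment and a brief medication check at visits already scheduled.

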10.0 CORRELATIVES/SPECIAL STUDIES

10.1 Sample Collection Guidelines

We plan on collecting and banking serial saliva and serum samples as well as tumor tissue.

10.1.1 Serum and Saliva Samples

10.1.1.1 These samples are mandatory. They will be obtained at Day 1 Cycle 1, Day 8 (+/- 4 days) Cycle 1, and Day 1 (+/- 4 days) of each subsequent Cycle while on therapy (see section 6.1).

10.1.1.4 Sample Transportation

- Whenever a specimen has been obtained (i.e. after a procedure, blood draw, oral rinse in clinic), sample will be labeled with the subject's de-identified study number and collection date, and the

study coordinator will transport the sample directly to the [name] laboratory.

10.1.2 Tumor Samples

10.1.2.1 We plan on obtaining tumor samples at screening, at Cycle 2 Day 1, and at progression.

- Screening biopsy sample is mandatory. This must be obtained within the 56 days prior to study treatment. No systemic therapy (i.e. immunotherapy) may have been administered since obtaining the biopsy, if so, a new biopsy is needed.
- Interim Biopsy at Cycle 2, Day 1 (+/- 7 days) is optional and will be offered if safe and clinically feasible
- Biopsy at the time of progression is mandatory however if the treating physician deems biopsy to be either unsafe or not clinically feasible, this must be documented and patient may forego repeat biopsy
- FFPE core biopsy is preferred, However, if not clinically feasible or safe to obtain a core biopsy, contact coordinating site PIs ([name]) as a block made from several FNA passes is acceptable.

[figure not shown]
10.1.3 [name] lab will receive and process samples. See Lab Manual for details

10.2 Assay Methodology

Hypothesis 1. *Specific genetic networks will correlate with response to Palbociclib-based therapy including patients with alterations in CDKN2A, CyclinD1, CDK4/6, RB and/or human papilloma virus. Thus, developing genetic biomarkers that predict response to this therapy will help identify the patients that would most benefit from early advancement to precision medicine trials.*

Experimental design: We will perform integrative targeted sequencing of all available tumor specimens to identify the distribution of lesions co-incident with commonly deregulated genes (e.g. *CyclinD1* and *CDKN2A* and their modifying genes) as well as the transcriptional programs deregulated in these tumors. We will utilize the knowledge gained from existing publicly available sequencing studies^{10,11,27-32} to perform targeted DNA and RNA sequencing in our cohort using our 250 gene MiOTOseq panel. We will also perform targeted RNA-Seq to assess the expression of genes used to classify tumors into immunogenic, classical, mesenchymal, basal or atypical molecular subtypes. The co-incidence of events will be correlated with immunohistochemical stains for established HNSCC biomarkers and correlations established between molecular events and clinical data.

1i. Preparation of biopsy specimens for targeted DNA and RNA sequencing. Collaborator [name] is a board certified pathologist and will identify representative FFPE sections with >50% tumor content, he has extensive experience in tissue specimen evaluation for molecular analysis³³⁻⁴⁵. We will use macrodissection to enrich for tumor content as needed. At least 3x10um sections per case will be cut for simultaneous DNA/RNA extraction using the Qiagen Allprep FFPE DNA/RNA kit and protocols optimized by our group to isolate assayable DNA (median 1.5 ug) and RNA (median 5.3 ug). As little as 9x10um sections from a single needle biopsy core yield sufficient DNA and RNA for the studies proposed herein. DNA and RNA will be quantified using the Qubit fluorometer.

1ii. Targeted next generation sequencing (NGS). Targeted, capture based NGS will be performed as shown in our preliminary data to the left using Ion Torrent or Illumina based sequencing (as in Fig 11). Briefly, barcoded libraries will be generated from 40ng of DNA per sample using our HNSCC-gene enriched custom Ion AmpliSeq panel, and the Ion Ampliseq Library Kit 2.0 with barcode incorporation. Templates will be prepared using the PGM Template OT2 Kitv2 on the Ion One Touch2; all protocols will be performed according to the manufacturer's instructions. Sequencing of multiplexed templates will be performed on Ion 318 chips using the Ion PGM 200

Sequencing Kitv2, sequenced to an average depth >100x. We routinely generate between 400-500 million aligned bases per 318 chip, yielding ~300-500x coverage for ~4-6 Oncomine Cancer Panel prepared templates. Mutation analysis will be performed in Torrent Suite 3.6, with alignment by TMAP using default parameters, and variant calling using the Torrent Variant Caller plugin using default low-stringency somatic variant settings. Variants will be annotated using ANNOVAR⁴⁶. Called variants will be filtered to prioritize likely candidate somatic drivers by removing the following variants: synonymous variants, those with frequencies >0.001 in ESP6500 or 1000 genomes, those with flow corrected read depths (FDP) <20, flow variant allele containing reads (FAO) <5 or variant allele fractions (FAO/FDP) <0.05. Copy number alterations will be identified as described^{34,47} (24, 39) using normalized read counts per amplicon with GC content correction and comparison to distributions from multiple unrelated normal FFPE derived genomic DNA samples. Gene-level copy number estimates will be determined by taking the coverage-weighted mean of the per-probe ratios, with expected error determined by the probe-to-probe variance; genes with $|Z| > 2.5$ with respect to both the normal pool and the internal error will be considered as gained or lost. Our team has established robust protocols for Ion Torrent sequencing, and has used the above methodology to characterize >600 tissue specimens. Alterations will be advanced for potential as HPV+ co-dependent drivers and correlated with RNA pathway alterations based on known roles in oncogenesis and H&N cancer, comparison to Oncomine (including TCGA and publicly available data) and COSMIC mutational data, and comparison to in house databases of driving lesions. Sanger sequencing, FISH, or qPCR will be performed to confirm prioritized alterations.

1iii. Targeted RNA-SEQ for molecular subtyping, gene fusion identification and pathway activity. Reverse transcription will be performed on 300ng of isolated RNA from each

tissue sample using gene specific priming with subsequent targeted RNA-SEQ using FFPE optimized assays as in Fig12. Genes have been selected to assess critical HNSCC pathways including HPV signaling status (including both E6 and E7 genes), deregulated CDK4/6 pathway genes, known HNSCC cancer fusions (through 5' and 3' assays for *FGFR-TACC3*⁴⁸ and *EGFR-ADACM* (TCGA-CV-6941), R-spondin⁴⁹, potential therapeutic targets in other malignancies (ie. 5' and 3' assays for ALK and RET overexpression), and housekeeping genes. Our team has extensive experience in RNA-SEQ, transcriptome evaluations and statistical analysis and will determine the frequencies of RNA signatures with DNA lesions as described^{33-40,50-58}.

Fig 12. Example of targeted RNA-seq from FFPE isolated RNA. A) Reverse transcription and targeted multiplexed PCR (Amplicseq) was performed on 20ng FFPE isolated RNA per sample on a cohort of macrodissected benign urothelium, non-invasive urothelial carcinoma (pTa) and invasive urothelial carcinoma (>pTa). Technical and biological replicates are indicated, as well as unique components isolated from the same case. For each sample, the log₂ total reads for each target gene (n=103) was normalized to the average log₂ total reads for 8 housekeeping genes. Median centered normalized target gene expression and samples were clustered using centroid linkage clustering and visualized as a heatmap. B) Scatter plot of target gene expression (log₂ normalized gene expression) for two biological replicates of normal urothelium (BL193A and BL193B, macrodissected from separate blocks). ($R^2=0.8986$).

sequencing studies will also be assessed by immunohistochemistry (IHC) if IHC grade antibodies are available. Staining and scoring will be completed as we described⁵⁹⁻⁶¹ with prioritization beginning with proteins found in the CDK4/6 pathway (e.g. CDK4, CDK6, RB, CyclinD1, etc.). We will leverage this data by integrating it with the sequencing data generated here to identify correlations between copy number, mutation and expression as well as HPV status using statistical methods described above.

Pitfalls, alternative strategies and future directions. We do not anticipate significant obstacles as we have extensive experience in tissue examination, NGS and integrative statistical analysis of molecular data in cancer as well as modeling of disease^{34,40,41,43,44,51,62}. Additionally, [name] is involved in several protocols that are sequencing tissue specimens as part of clinical trials or protocols, including the MiOncoseq-SU2C program^{48,63}. The cohort size is based on conservative statistical estimates as noted to reach independent correlative endpoints. Targeted sequencing has been proposed to enable a focused analysis of tumors with limited DNA/RNA yields. However, we have had success sequencing whole exomes from FFPE tissues from large quantities of DNA using multiple platforms and may implement these if the technology becomes robust enough during the course of the proposal for smaller quantities of DNA. Similarly, we are currently evaluating whole transcriptome analysis as an alternative to targeted RNA-SEQ from FFPE in samples with sufficient RNA yield. Overall, we expect that completion of this Aim will identify the co-incident frequency of commonly deregulated pathways on the DNA and RNA levels that will predict response to standard therapy. Importantly, we will create a molecularly characterized TMA of specimens from this clinical trial to assess correlations between genetic and protein expression status. Taken together, this Aim will provide a wealth of data and resources for future studies

and provide a comprehensive data set correlating genetic aberrations with clinical outcome in this trial setting.

Hypothesis 2: Cancer response to therapy can be detected in saliva and serum biospecimens collected at routine interval time points and will identify tumor response earlier than interim imaging.

Correlative Justification

Less than 40% have a response (SD, PR, CR) to chemotherapy in R/M which currently only be identified by interval imaging after approximately 8-12 weeks of therapy. As patients are at risk for treatment failure, a non-invasive biomarker for detecting response earlier in therapy is of extreme importance. The measurement of serum and saliva circulating tumor ctDNA as a biomarker for recurrence may be an important, noninvasive method to detect treatment responses. Our group and others have identified HPV and mutant ctDNA in both the blood and saliva samples of patients with advance or recurrent HNSCC, suggesting this noninvasive biomarker as a way to measure disease response to therapy. Finally, using data generated from the targeted next generation sequencing on tumor specimens from above, we can prioritize evaluable somatic mutations in ctDNA from both the blood and saliva of each patient for targeted sequencing studies as well as monitor for the occurrence of mutations common in tumors that become resistant to Palbociclib treatment. Therefore, our goal is to collect longitudinal samples of saliva and serum as a part of our trial to determine if serum and saliva biomarkers can predict response to therapy and also identify emergence of resistant clones.

